2. Patients undergoing elective primary ankle or hindfoot surgery (ankle arthrodesis, subtalar arthrodesis, triple arthrodesis, total ankle arthroplasty, peroneal tendon debridement/transfer, Cavus Reconstruction, Medial Displacement Calcaneal Osteotomy, Dwyer Osteotomy)

Exclusion Criteria:

1. Patients who are undergoing revision surgical procedure
2. Patients who have taken opioid pain medications in the past 3 months prior to surgical procedure
3. Patients who have allergies to any of the medications or components of medications investigated in the study
4. Patients currently incarcerated
5. Patients who cannot read and speak English

Study Recruitment:

The study investigators will identify potential study participants in the outpatient clinic. The patients that meet inclusion criteria will be approached by the physician investigator, research coordinator(s), and/or research assistant(s) during their orthopaedic clinic visit and will be asked to participate in the study. After hearing the study explanation, if the patient is interested in participating, the physician investigators, research coordinator(s) and/or research assistant(s) will review, with the patient, the informed consent form asking authorization to access/use their PHI. The patient will sign and date the form after all questions have been satisfactorily answered by the study team. Recruitment materials will consist of the informed consent form.

Study Duration:

Approximate Duration of Subject Participation:

Patients will participate in the study for approximately 3 months – from initial recruitment to end of participation.

Approximate Duration of Study:

The study will be completed in approximately 12 months. The end of the study is the last visit of the last subject, or end of collection of data from the patient's electronic health record.

Procedures:

Patients who meet inclusion criteria will undergo a selection process, and if they choose to participate will be randomized into one of two groups. The randomization scheme will be created with the use of an internet based randomization website (<https://www.randomizer.org>). Qualifying subjects will be randomized into one of two groups prior to their surgery:

PI: [name]

IRB# 2018-0486

Version 1.1 (07/23/2019)

1. Liposomal Bupivacaine Group**a. Pre-operative**

i. No peripheral nerve block will be given

b. Intraoperative

i. Local infiltration of 20cc of Liposomal Bupivacaine infiltrated to the surgical area

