Statistical analysis will be performed by [name]

Data Management

Data to be Collected:

The following data will be collected from the EMR:

- PHI elements (will not be included in final dataset)
- Medical Record Number (MRN)
- Name
- Date of Birth
- Patient Demographics (Age, gender, weight, height, Body Mass Index (BMI))
- Medical History
- Narcotic use history
- Inflammatory or Rheumatoid Arthritis
- Complications / AE
- Wound Hematoma
- Superficial wound infection (defined as any prescription for post-op antibiotics)
- Wound complications
- Deep infection (defined as need for surgical irrigation and debridement)
- Crossover
- Number of patients randomized to liposomal bupivacaine group that request peripheral nerve block
- Unscheduled healthcare contact and reason for contact
- Phone calls
- Emails
- MyGeisinger Messages
- Unscheduled clinic visits
- ED visits
- Dates
- Date(s) and information related to admission, surgery, and discharge
- Date(s) and information related to clinic visits

The following data will be collected during the patient clinic visits:

- VAS Pain Scale (0-10)
- Pain journal from post-operative days 0-7 including pain medication utilization and pain scores

Data Collection and Storage

The data points outlined above will be reviewed and collected from the EMR by the study coordinator(s), project coordinator(s) and/or co-investigators. A data request will be submitted to the BC Data Broker, an independent person from the study team.

A member of the IRB-approved Geisinger study team will perform a manual chart review for data points not captured during the BC data pull. A member of the IRB approved study team will randomly assign

PI: [name]

IRB# 2018-0486

Version 1.1 (07/23/2019)

study ID numbers in order to protect the identity of the subject. After the dataset has been de-identified, an IRB-approved study team member will forward the completed dataset to [name] for analysis. All study data will be kept in GHS maintained username/password-protected computer files and hard copy data will be double locked and accessible only to the study investigators in the locked office of the Study Coordinator. Only group-level information without personal identifiers will be included when presenting results or submitting manuscripts for publication.

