Personal or sensitive information that could be potentially damaging to participants (e.g. relating to illegal behaviors, alcohol or drug use, sexual attitudes, mental health, etc.) will not be collected. With concerns to HIV/AIDS status, if the status is already in the participant's medical record it will be reported into the CRF as a "yes" or "no," otherwise it will be reported in the CRF as "not assessed." Regarding collected mental health information that could be potentially damaging to participants, participants indicating that they are very depressed, thus raising concern regarding their mental state, will be referred to their primary care physician.

No PHI will be shared outside of the IRB approved study staff.

Records Retention

Records of data generated in the course of the study will be kept indefinitely and may be used for future research purposes.

Adverse Event Reporting

Clinical adverse events (AEs) will be monitored throughout the study. All AEs will be reported to the institutional review board (IRB) according to IRB policy. The date and time of onset and outcome, course, intensity, action taken, and causality to study treatment will be assessed by the study PI.

Definitions

An adverse event (AE) is any untoward, undesired, or unplanned event in the form of signs, symptoms, disease, or laboratory or physiologic observations occurring in a person given a test article or in a clinical study. The event does not need to be causally related to the test article or clinical study.

Adverse Events related to Elective Ankle and Hindfoot Surgery:

- Infection
- Wound healing issues
- Persistent pain
- Peripheral nerve injury
- Arterial injury
- Wound complications

A protocol-related adverse event is an AE occurring during a clinical study that is not related to the test article, but is considered by the investigator or the medical monitor (or designee) to be related to the research conditions, i.e., related to the fact that a subject is participating in the study. For example, a

protocol-related AE may be an untoward event occurring during a washout period or an event related to a medical procedure required by the protocol.

Recording and Reporting

A subject's AEs will be recorded and reported from the signing of the informed consent form to end of study period.

Protection of human subjects

Informed Consent

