The investigator will provide for the protection of the subjects by following all applicable regulations. The informed consent form will be submitted to the IRB for review and approval. Prior to having any study procedures performed, the patient will be asked to read and then sign the informed consent form if they agree to participate in the study. The subject will receive a copy of the signed/dated informed consent form for their records. The original copy of the informed consent form will be scanned into the subject's EMR and the hardcopy will be filed in the subject's study binder. The rights and welfare of the subjects will not be affected. We are requesting to observe and record variables that are normally collected and entered into the patient's EMR in the course of standard clinical care. The purpose of recording data for this prospective study (in addition to the EMR) is simply to ensure that discrete, standardized format (since some variables, while stored in the EMR, may appear in physician notes as free text).

There is very little to no risk associated with this study. The risk to study participants is related to accidental disclosure of PHI (i.e. MRNs, dates). Any time information is collected for a study there is a small risk of breach confidentiality. However, this risk is not greater than the risk that already exists in clinical settings when handling medical data.

A partial waiver of HIPAA authorization is being requested for this study. A waiver is necessary for the research to be practically conducted because the research team must review the patient's PHI to determine eligibility. The research team would be unaware of potential eligible patients without reviewing that patient's relevant medical information. If the patient does not meet eligibility criteria, they will not be approached to partake in the study. While PHI is being requested, it is the minimal amount necessary to ensure patients are eligible based on the inclusion criteria.

Protection of Human Subjects Against Risks

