The investigator will provide for the protection of the subjects by following all applicable regulations. Anticipated risks in this study are minimal. This study will not affect patient care or access to care. The major risk to human subjects in this study is the accidental disclosure of PHI. In this regard, the assignment of a coded test ID number to each individual participant and the protocol of providing only the necessary associated clinical information to the remainder of the research team mitigate this risk.

All study data will be kept in Geisinger Health System maintained username/password-protected computer files and hard copy data will be double locked and accessible only to the study investigators. Only group-level information without personal identifiers will be included when presenting results or submitting manuscripts for publication.

Publication Plan:

We plan to prepare and submit the results of this study for presentation at national meetings and in peer-reviewed journals.

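### The risk statements contradict a design that randomises analgesia, and the complication fields omit nerve, pain and arterial events that the protocol lists elsewhere

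*Protocol*

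**What the plan says.** On risk, the Informed Consent section of the protocol states: "There is very little to no risk associated with this study". The one risk it names is inadvertent release of identifiable health information. It describes the research as record-taking: "We are requesting to observe and record variables that are normally collected and entered into the patient's EMR in the course of standard clinical care". In the next section, Protection of Human Subjects Against Risks, the protocol says "This study will not affect patient care or access to care", calls the anticipated risks minimal and adds "The major risk to human subjects in this study is the accidental disclosure of PHI".

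On design, Procedures randomises patients to one of two analgesic regimens. In the liposomal bupivacaine arm "No peripheral nerve block will be given"; in the block arm there is no local infiltration. Both arms get the same protocol-specified discharge medication, which is expressly excepted from the surgeon's standard practice.

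On harms, there are two lists:
- **Data to be Collected, Complications / AE:** four items, namely "Wound Hematoma", superficial wound infection, wound complications and deep infection.
- **Adverse Event Reporting**, headed "Adverse Events related to Elective Ankle and Hindfoot Surgery": six items, namely infection, wound healing issues, persistent pain, peripheral nerve injury, arterial injury and wound complications.

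Specific Aim 5 and the fourth secondary endpoint compare complications between the arms.

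**The concern.** There are two linked problems.

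First, the risk text describes an observational study, whereas this is an interventional one. Even if both techniques are routine at the sites, the study replaces clinical choice with chance in deciding which one a patient gets. That affects care, and the risks of the assigned technique then belong in the study's risk statement. A review board reading only the human-subjects sections would be weighing a different study from the one in Procedures.

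Second, the named complication fields do not follow the randomised contrast. The planned difference between arms is the analgesic technique, so harms of that technique are where a difference in complications is most plausible. The named fields cover wound and infection events, and the protocol's two lists disagree about nerve injury, persistent pain and arterial injury. If those events depend on unprompted reporting, they may be missed, or noticed unevenly: Procedures states that the surgeon is not blinded.

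**Working it through.** No arithmetic beyond counting applies, because the protocol gives no figure on this point. The check sets its sections side by side.

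**Step 1: risk text against design.**

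| Human-subjects sections | Elsewhere in the protocol |
|---|---|
| Study has no effect on care | Randomisation decides the analgesic technique (Procedures) |
| Study observes and records routine variables | Block withheld in one arm, infiltration withheld in the other; discharge medication set by the protocol (Procedures) |
| Data disclosure is the major risk | The investigator rates each adverse event for its relation to study treatment (Adverse Event Reporting) |

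Each row conflicts. In the third, rating an event against study treatment presupposes a study treatment that could cause harm. Data to be Collected also counts liposomal-arm patients who ask for a block, so the protocol itself expects that some patients may want the technique their assignment withheld.

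**Step 2: list against list.**

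| Event | Data to be Collected | Adverse Event Reporting |
|---|---|---|
| Haematoma | named | not named separately |
| Infection | superficial and deep | named |
| Wound problems | named | named (two items) |
| Persistent pain | absent | named |
| Peripheral nerve injury | absent | named |
| Arterial injury | absent | named |
| Event named as a harm of the block or infiltration | absent | absent |

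By count, 4 of 4 items in the first list are wound or infection events. In the second, 6 − 3 = 3 of 6 are, and the other 3 have no counterpart in the first. Nerve injury appears in the second list, but under a heading that ties it to the surgery.

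**Step 3: what else would catch these events.** Adverse Event Reporting defines an adverse event broadly, without requiring a causal link, and records events from consent to the end of the study period. The Study Time and Events Table schedules adverse event and complication reporting on the day of surgery, at 0, 6 and 12 hours, and at 2 and 6 weeks. The follow-up text asks for complications of any kind to be noted. A block-related or anaesthetic-related event would therefore be recorded if it is reported. What is missing is a named field that prompts for it in the same way in both arms.

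**The case against.** The strongest reply is that safety capture is already complete. All adverse events are recorded at every visit from the day of surgery, in both arms, with causality assessed, and nothing says that the four items in Data to be Collected are exhaustive. Those items are data taken from the medical record, which is only one source. Inadequate pain relief is also well covered: pain is the primary endpoint, opioid use is a secondary endpoint, requests for a block in the liposomal arm are counted, and unscheduled contacts are reviewed for their reason. On this view the risk wording is a matter for the review board and changes no estimate.

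Much of this stands, and it rules out several stronger readings that a reader might infer:
- **That harms of the two techniques are not compared.** Specific Aim 5 and the fourth secondary endpoint do compare complications.
- **That Aim 5 is analysed only from the four-item list.** No section says so, and tabulation may be left to an analysis plan that is not shown.
- **That participants are told data disclosure is the only risk.** The consent form is not shown; the statements are protocol text.
- **That the gap can be sized by what zero events in an arm would exclude.** Such a bound reflects sample size and would be the same for a listed event. It would also assume an equal split of the approximately 50 patients, which the protocol does not state.

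Two things survive the reply. General reporting does not reconcile two lists in one protocol that disagree, and passive capture is weaker than a defined field completed for every patient. Nor does any of it make the statement about care true.

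**Conclusion.** The point holds in two parts. The contradiction between the risk statements and the randomised design is plain from the text and rests on no assumption. No analysis plan could cure it, because the statement is in the protocol and is wrong for this design.

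The second part is a risk of under-ascertainment, not a demonstrated loss. Three events on one list have no named field in the other, and technique-related harm is named in neither. How far this would affect Aim 5 cannot be estimated from the document, which gives no event rates. The judgement assumes that events with a defined field are recorded more completely and more evenly between arms than events left to general reporting. It does not depend on which source Aim 5 will use. The change is worth making before recruitment goes far, but the point does not undermine the primary pain comparison.

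**What to change.** 1. Reconcile Informed Consent and Protection of Human Subjects Against Risks with Procedures. State that the study assigns the analgesic technique by randomisation and sets the discharge medication, and that the risks of the assigned techniques apply alongside the data-disclosure risk. Remove the statement that care is unaffected and the description of the study as only observing and recording.
2. Align the Complications / AE list in Data to be Collected with the Adverse Event Reporting list by adding peripheral nerve injury, persistent pain and arterial injury.
3. Add one field for events attributed to the block or to the local anaesthetic.
4. Complete these fields for every patient in both arms, with the same definitions and at the same scheduled times, so that a blank can be told apart from an absence.

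The cost is a few form fields and a corrected risk paragraph submitted to the review board. No visit, treatment or sample size changes.
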